## 3.0 Scientific Endpoints\*

*2.1 Describe the scientific endpoint(s), the main result or occurrence under study.*

*NOTE: Scientific endpoints are outcomes defined before the study begins to determine whether the objectives of the study have been met and to draw conclusions from the data. Include primary and secondary endpoints. Some example endpoints are: reduction of symptoms, improvement in quality of life, or survival. Your response should **not** be a date.*

Response:

The primary endpoint is to determine whether there are group differences in grocery purchases among adults randomized to the Online or Defaults interventions or control group. Primary analyses will examine differences in the study groups' grocery purchases, including total calories, carbohydrates, and sugar (total sugar and/or added sugar), and overall nutritional quality of foods and beverages purchased at post-test and throughout the study period.

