## 2.0 Objectives\*

*2.1 Describe the purpose, specific aims, or objectives of this research.*

Response:

The goal of this study is to test novel approaches informed by behavioral economics to promote healthier grocery shopping among adults diagnosed with type 2 diabetes or at increased risk of developing type 2 diabetes, defined as a diagnosis of prediabetes or meeting criteria for increased risk of developing type 2 diabetes as determined by the American Diabetes Association Type 2 Diabetes Risk Test. The specific aims are: (1) to test effects of *Online* and *Defaults* grocery shopping interventions on participants' grocery purchases and (2) to explore effects of the *Online* and *Defaults* interventions on participants' spending during grocery shopping.

*2.2 State the hypotheses to be tested, if applicable.*

*NOTE: A hypothesis is a specific, testable prediction about what you expect to happen in your study that corresponds with your above listed objectives.*

Response:

It is hypothesized that (1a) purchases made by adults in the Defaults group will be lower in calories, carbohydrates, and sugar (total sugar and/or added sugar) and higher in nutritional quality (DASH diet score) at post-test versus other study groups, (1b) adults in the Defaults group will show the greatest increases in nutritional quality versus other study groups, (1c) the Online group will have intermediary results between Defaults and Controls, and (2) there will be no difference in total dollars depicted on receipts across study groups during the intervention period (i.e., the costs of online shopping will be offset by effects of the Online and Default interventions).

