## 5.0 Study Design\*

5.1 Describe and explain the study design (e.g. case-control, cross-sectional, ethnographic, experimental, interventional, longitudinal, observational).

Response:

This study has an experimental design. Participants will be randomly assigned to 1 of 2 interventions or a control group in which they will shop in-person as usual. Stratification factors will be sex and diabetes status: type 2 diabetic vs. at risk for type 2 diabetes, defined as a diagnosis of prediabetes or meeting criteria for increased risk of developing type 2 diabetes as determined by the American Diabetes Association Type 2 Diabetes Risk Test. In all groups, recipe cards that follow the evidence-based DASH diet and correspond to dietary recommendations for diabetic patients will be provided. The *Online* intervention will utilize online grocery shopping (shopping at a local grocery store via Instacart) to promote healthier purchasing, removing visceral factors that can lead to impulse purchases in stores. The *Defaults* intervention will augment this intervention, showing participants a default cart when they log into their accounts. They will be told that their cart has been filled with items that conform to a diet appropriate for diabetes prevention, management, and overall health and can be used to make the recipes from the provided recipe cards, and that they may modify it as they like.

At baseline, all participants will complete a survey online or via phone and then will grocery shop in-person as usual. Participants will then be randomized and receive further instructions. For the next 3 weeks, they will receive recipe cards and shop in accordance with their assigned study group. The following week (post), they will shop using the method of their choice (in-person, online) and complete a survey again. Household receipt data will be collected throughout the study. The baseline period will also serve as a run-in period, and participants who do not comply with study guidelines for baseline procedures (including guidelines for receipt submission) will not be randomized for further participation. Primary analyses will examine intervention effects on grocery purchases, with additional analyses on spending and dietary intake. All participant interactions will occur online or via phone.

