## **19.0 Data Management and Analysis\***

*19.1 Describe the data analysis plan, including any statistical procedures. This section applies to both quantitative and qualitative analysis.*

Response:

Linear mixed models will be used to test effects of the interventions on total calories, carbohydrates, sugar (total sugar and/or added sugar), and nutritional quality of grocery purchases, with study group, time, and their interaction as factors. Primary comparisons will be between-groups comparisons of these variables at post-test. We will also examine whether these variables differ overall by study group and whether changes in these variables differ by study group. We will conduct each analysis once for the total cart and then again examining these variables relative to household size and for items that the respondent indicated they would be consuming. We will conduct parallel analyses with total dollars spent each week and with DASH diet scores as outcomes to examine effects on spending and intake. We will also explore whether effects differ for participants with prediabetes vs. diabetes and whether results change when adjusting for food purchases beyond the target stores. Finally, we will test for relationships between purchases (calories, carbohydrates, and sugar (total sugar and/or added sugar)) and intake (DASH diet scores). We will also explore whether results differ when considering shopping trips completed by the participant only (vs. all trips for the household).

*19.2 If applicable, provide a power analysis.*

*NOTE: This may not apply to certain types of studies, including chart/records reviews, survey studies, or observational studies. This question is asked to elicit whether the investigator has an adequate sample size to achieve the study objectives and justify a conclusion.*

Response:

To estimate the sample size needed for this study, effect sizes from the most similar existing study were used: a proof-of-principle study examining the effects of defaults, incentives, and education strategies on healthfulness of grocery purchases among undergraduate students (Coffino & Hormes, 2018, Obesity). Based on the observed differences in calories purchased at post-test between defaults and education control groups (Cohen's  $d=0.96$ ), 15 participants would be needed for the primary comparison in the present study, with  $\alpha=.05$  and  $\text{power}=.80$ . We repeated this analysis using the difference between controls and

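### Sections 3.0 and 19.1 make four purchase outcomes primary across three arms with no multiplicity control, and do not adopt the lead comparison that 19.2 already implies

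*Combined protocol and SAP*

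**What the plan says.** Section 5.0 sets up three arms: "Participants will be randomly assigned to 1 of 2 interventions or a control group". Section 3.0 describes the primary analyses as group differences in purchases, "including total calories, carbohydrates, and sugar (total sugar and/or added sugar), and overall nutritional quality of foods and beverages purchased", both at post-test and throughout the study period. No outcome is put ahead of the others, and sugar may be total, added or both.

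The hypotheses in 2.2 reach all three arm pairs. Hypothesis 1a sets Defaults against each other arm; for quality, purchases are to be "higher in nutritional quality (DASH diet score) at post-test versus other study groups". Hypothesis 1c says that "the Online group will have intermediary results between Defaults and Controls".

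Section 19.1 specifies linear mixed models with group, time and their interaction, and states: "Primary comparisons will be between-groups comparisons of these variables at post-test". It also plans tests of overall group differences and of differences in change, without calling them primary. It then multiplies the analyses: "We will conduct each analysis once for the total cart and then again examining these variables relative to household size and for items" the respondent expects to consume.

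An alpha of .05 appears only in 19.2. There the first calculation is "Based on the observed differences in calories purchased at post-test between defaults and education control groups" (d = 0.96), and that contrast is called the primary comparison. A second calculation uses the earlier study's intermediary group against controls (d = 0.44), because of interest in the Online arm. It gives 54, which is then raised to a ceiling of 100.

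**The concern.** A reader of 3.0 and 19.1 cannot tell which single result decides Aim 1. Any of 12 post-test comparisons could be reported as a primary finding, and the nominal 5% does not describe the chance that at least one is significant by luck.

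Two further gaps widen the choice. Section 3.0 counts the whole study period as primary, while 19.1 reserves that status for post-test. The sugar measure is also unsettled, and if both versions are analysed the 12 tests become 15. A choice made after the data are in could not be told apart from one made in advance.

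**Working it through.** **Inputs from the documents.** Four primary outcomes (3.0); three arms (5.0), hence 3 pairs (2.2); three versions of each analysis (19.1); alpha .05, power .80, d = 0.96 and 0.44, sample sizes 15 and 54, ceiling 100 (19.2).

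**Assumptions.** Two-sided tests; no effect anywhere; correlations between outcomes and between versions, since the documents give none. The arm sizes used are 54/3 = 18 and 100/3 ≈ 33; 19.2 does not say whether 54 is a total.

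1. *The plan's own figures.* No family-wise error rate is stated, so only the sample sizes can be reproduced. Two-sample formulas do not give both (two-sided, normal approximation: 18 and 82 per arm). A group × time F test does, as total N, with f = d/2, 3 groups, and 2 time points correlated 0.5 (both assumed): λ = f²·N·2/(1 − 0.5).
   - d = 0.96, N = 15: λ = 0.48² × 15 × 4 = 13.8; power 0.84.
   - d = 0.44, N = 54: λ = 0.22² × 54 × 4 = 10.5; power 0.81.

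   On this reading the .05 belongs to one overall test of one outcome, not to a family of pairwise comparisons.

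2. *Count of primary tests.* 4 outcomes × 3 pairs = 12 at post-test on the total cart.

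3. *Ceiling under independence.* 1 − 0.95¹² = 0.46. This is too high, because the pairs share arms.

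4. *Simulation with shared arms* (10,000 to 20,000 trials per setting, pooled-variance t tests, 18 and 33 per arm):

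| Tests | Outcome correlation | At least one p < .05 | With an overall group test first |
|---|---|---|---|
| 1 outcome × 3 pairs | n/a | 12% | 5% |
| 4 outcomes × 3 pairs | 0 | 40%–41% | 18%–19% |
| 4 outcomes × 3 pairs | 0.5 | 34%–35% | 16% |
| 4 outcomes × 3 pairs | 0.8 | 26% | 11%–12% |

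   The last column agrees with four independent overall tests: 1 − 0.95⁴ = 0.185.

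5. *Adding the two repeats.* 12 × 3 = 36 tests. At 18 per arm the range is 39% (outcomes correlated 0.8, versions 0.9) to 79% (all uncorrelated). In an illustrative case with calories, carbohydrates and sugar correlated 0.8 and DASH −0.2 with each, it is 62%, 57% and 47% for correlations between versions of 0.5, 0.7 and 0.9.

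6. *Price of adjusting all 12 equally.* At 18 per arm and d = 0.96, d√(n/2) = 0.96 × 3 = 2.88. At .05, Φ(2.88 − 1.96) = 0.82 (0.80 by t test). At .05/12 = .0042, Φ(2.88 − 2.865) = 0.51. One named primary test avoids this loss.

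7. *Online vs Control under two secondary schemes* (d = 0.44; Defaults vs Online taken as 0.96 − 0.44 = 0.52, common SD assumed). Tested alone at .05, power is 25% at 18 per arm and 42% at 33. Placed last in a fixed sequence after the two Defaults comparisons, it is about 3% to 4% and 16%. In a Holm pair the stricter step is .025 (z = 2.241), which gives at least about Φ(0.44 × 3 − 2.241) = 0.18 at 18 per arm and Φ(0.44 × √16.5 − 2.241) = 0.32 at 33.

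**The case against.** The best defence is that the plan has more structure than a bare count suggests. Section 19.2 names a primary comparison, 19.1 fixes post-test as the main time point and lists the total cart first, and the mixed model could be read as an overall test before any pairwise one. This partly stands: a lead test is implied. But neither 3.0 nor 19.1 adopts it, and no overall test is made a condition for the pairwise ones. Even if it were, the error rate would be two to four times nominal.

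Four stronger readings are tempting and not supported:

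- *That a false positive is more likely than not.* For the 12 tests the figure stays below one half throughout. It passes one half only for most settings of the 36-test family, and 19.1 does not label the two repeats primary.
- *That the plan commits to testing everything at 5%.* The level comes from the power section and the absence of any adjustment; 19.1 states no decision rule. Hypothesis 1a can also be read as a joint claim about all four outcomes.
- *That only calories for Defaults vs control has a power basis.* Section 19.2 gives a second one for the intermediary group, and that one drives the sample size.
- *That the sugar measure was left open to suit the results.* Revision 11 in the revision history gives a practical reason: added sugar may be hard to obtain with the nutritional software in use.

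The pilot argument also carries some weight. Section 8.4 refers to the study's pilot nature, and 12.1 looks ahead to larger work. That lowers the stakes but does not supply error control, and 2.1 still sets out to test effects.

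**Conclusion.** The point holds. Four outcomes are primary for three arm pairs without multiplicity control, 3.0 and 19.1 disagree on the primary time window, and the comparison singled out in 19.2 is not carried into either section. On the stated assumptions, the chance of at least one false positive over the 12 post-test total-cart tests is about 26% to 41% rather than 5%, or 11% to 19% if an unstated overall test came first. The range depends on outcome correlations that the documents do not give. The excess over 5% does not: it appears at every correlation tried. Given the pilot setting, this should be fixed but is not disqualifying.

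**What to change.** In 3.0 and 19.1, in matching words:

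- **Primary:** calories purchased at post-test, total cart, Defaults vs Control, two-sided 5%. This is the outcome and contrast used in 19.2.
- **Key secondary:** Defaults vs Online and Online vs Control on the same outcome, Holm-adjusted as a pair. A fixed sequence ending with Online vs Control should be avoided: it would nearly remove a question that 19.2 uses to size the study.
- **Secondary:** carbohydrates, total sugar and DASH quality of purchases, Holm-adjusted across their pairwise comparisons (3 × 3 = 9 tests).
- **Sugar:** fix the outcome as total sugar, for the software reason given in revision 11; added sugar becomes exploratory.
- **Supporting:** the household-size and respondent-consumed versions, and the overall and change contrasts. This also settles the time-window conflict in favour of post-test.

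The cost is analysis wording, with no new participants or procedures. Carbohydrate, sugar and DASH findings can no longer be called primary, hypothesis 1b (greatest increase in quality) rests on a supporting analysis, and the Online comparisons lose some power to the Holm step. For Online vs Control that is from 25% to no lower than about 18% at 18 per arm, and from 42% to no lower than about 32% at 33. The 5% then applies to the primary claim, and each secondary family carries its own 5%.

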## 4.0 Background\*

*4.1 Provide the scientific or scholarly background, rationale, and significance of the research based on the existing literature and how it will contribute to existing knowledge. Describe any gaps in current knowledge. Include relevant preliminary findings or prior research by the investigator.*

Response:

Millions of deaths are caused by diabetes, and impacts on health expenditures are staggering, with \$727 billion spent in 2017. Dietary approaches are recommended for weight control and diabetes prevention and management, but modern environments, characterized by plentiful, unhealthy foods, pose challenges to selecting a healthy diet. Modifications to the food environment can address these barriers by making healthier choices more automatic and reducing the need for self-control.

Behavioral economics offers a framework for modifying the food environment to encourage individuals with diabetes to select foods that align with diabetic diet goals. The standard dietary approach to diabetes involves educating people in a clinical setting but does not prepare them to make purchasing decisions under normal conditions. Decision-making is affected by visceral factors, including hunger and strong emotions, which can lead to impulse purchasing. Rather than expecting humans to behave rationally, behavioral economics aims to make the healthy choice the easy choice. For example, people tend to accept default options rather than requesting alternatives, offering the potential to encourage healthier behaviors by positioning them as automatic defaults.

Such strategies have been applied effectively in many domains (e.g., organ donation; Johnson & Goldstein, 2003) but have seldom been used to promote health during grocery shopping, which is the leading source of sugar-sweetened beverages and nutrient-poor foods (An & Maurer, 2016). One recent study randomized undergraduates to grocery shop online, receiving either: 1) nutrition education, 2) a financial incentive for selecting healthy foods, or 3) a default shopping cart with healthy foods, which they could alter as desired. The default group chose healthier foods than education controls, with no effect of incentives. This study supports the promise of defaults to encourage healthier purchases when grocery shopping and highlights a need for ecologically-valid studies in populations with diet-related diseases. The present study will fill this gap by testing online grocery shopping and defaults as potential mechanisms

to promote adherence to a diabetic diet among adults with diabetes or at risk of developing diabetes.

These strategies have translational significance as they could be incorporated into clinical treatment: e.g., by “prescribing” online grocery shopping if the Online intervention is efficacious, and/or working with dietitians to generate default carts catering to different lifestyles and disseminating this information in clinical settings and/or via partnerships with grocery stores. As such, the proposed interventions have the potential to improve dietary intake, glucose regulation, weight, and medication needs among diabetic patients. The study team has the substantive expertise needed to examine this question, including a history of behavioral economics, diabetes, grocery shopping/retail, and community-based research (e.g., Anzman-Frasca et al., 2018; Epstein & Saelens, 2000; [name] et al., 2018).

## 5.0 Study Design\*

5.1 Describe and explain the study design (e.g. case-control, cross-sectional, ethnographic, experimental, interventional, longitudinal, observational).

Response:

This study has an experimental design. Participants will be randomly assigned to 1 of 2 interventions or a control group in which they will shop in-person as usual. Stratification factors will be sex and diabetes status: type 2 diabetic vs. at risk for type 2 diabetes, defined as a diagnosis of prediabetes or meeting criteria for increased risk of developing type 2 diabetes as determined by the American Diabetes Association Type 2 Diabetes Risk Test. In all groups, recipe cards that follow the evidence-based DASH diet and correspond to dietary recommendations for diabetic patients will be provided. The *Online* intervention will utilize online grocery shopping (shopping at a local grocery store via Instacart) to promote healthier purchasing, removing visceral factors that can lead to impulse purchases in stores. The *Defaults* intervention will augment this intervention, showing participants a default cart when they log into their accounts. They will be told that their cart has been filled with items that conform to a diet appropriate for diabetes prevention, management, and overall health and can be used to make the recipes from the provided recipe cards, and that they may modify it as they like.

At baseline, all participants will complete a survey online or via phone and then will grocery shop in-person as usual. Participants will then be randomized and receive further instructions. For the next 3 weeks, they will receive recipe cards and shop in accordance with their assigned study group. The following week (post), they will shop using the method of their choice (in-person, online) and complete a survey again. Household receipt data will be collected throughout the study. The baseline period will also serve as a run-in period, and participants who do not comply with study guidelines for baseline procedures (including guidelines for receipt submission) will not be randomized for further participation. Primary analyses will examine intervention effects on grocery purchases, with additional analyses on spending and dietary intake. All participant interactions will occur online or via phone.

## 6.0 Study Intervention/Investigational Agent

1.1 Description: *Describe the study intervention and/or investigational agent (e.g., drug, device) that is being evaluated.*

Response:

This study does not involve drugs or devices; however, there will be two interventions in this study. The first intervention is the *Online* intervention, which will utilize online grocery shopping (shopping at a local grocery store via Instacart) to promote healthier purchasing, removing visceral factors that can lead to impulse purchases in stores. The second intervention, the *Defaults* intervention, will augment the *Online* intervention, showing participants a default cart when they log into their accounts. They will be told that their cart has been filled with items that conform to a diet appropriate for diabetes prevention, management, and overall health and can be used to make the recipes from the provided recipe cards, and that they may modify their cart as they like.

6.1 *Drug/Device Handling: If the research involves drugs or device, describe your plans to store, handle, and administer those drugs or devices so that they will be used only on subjects and be used only by authorized investigators.*

- *If the control of the drugs or devices used in this protocol will be accomplished by following an established, approved organizational SOP (e.g., Research Pharmacy SOP for the Control of Investigational Drugs, etc.), please reference that SOP in this section.*

Response:

N/A, this study does not involve drugs or devices.

6.2 *If the drug is investigational (has an IND) or the device has an IDE or a claim of abbreviated IDE (non-significant risk device), include the following information:*

- *Identify the holder of the IND/IDE/Abbreviated IDE.*
- *Explain procedures followed to comply with sponsor requirements for FDA regulated research for the following:*

	Applicable to:		
FDA Regulation	IND Studies	IDE studies	Abbreviated IDE studies
21 CFR 11	X	X	
21 CFR 54	X	X	
21 CFR 210	X		
21 CFR 211	X		
21 CFR 312	X		
21 CFR 812		X	X
21 CFR 820		X	

Response:

N/A, this study does not involve drugs or devices.

